2.13.2.2 Treatment groups to be included at interim analysis

At the interim analysis, efficacy and safety outputs will be provided in blinded fashion, in other words, the study treatment group of interest in this interim analysis is defined as “Any ligelizumab treatment” since all subjects will be receiving same treatment (ligelizumab 120mg) starting from Week 12.

Additional listings maybe prepared and reported elsewhere in separate documents (e.g., SCE, SCS) by the QGE031C2302 and QGE031C2303 unblinded team to link unique subject identification numbers and treatment groups between the proceeding studies and the extension study, if needed.

2.13.2.3 Patient disposition, demographics, and other baseline characteristics for interim analysis

Demographic (defined in Section 2.3) and other baseline data including disease characteristics (listed below) will be summarized descriptively for all participants in the Safety Set (SAF), and the participants included in the subpopulations defined in Section 2.13.2.1. Categorical data will be presented as frequencies and percentages. For continuous data, mean, standard deviation, median, minimum, and maximum will be presented. For selected parameters, 25th and 75th percentiles will also be presented.

Preceding study baseline is defined as the baseline in study CQGE031C2302, CQGE031C2303, CQGE031C2202 and CQGE031C1301. Extension study baseline is defined in study CQGE031C2302E1 Section 2.1.1.4.

2.13.2.3.1 Disease characteristics at baseline (defined in study Section 2.1.1.4)

- CU Index category
- [REDACTED]
- UAS7 score
- Duration of CSU – collected at Visit 201
- AAS7 score
- Angioedema occurrence (Yes/No) based on medical history

2.13.2.3.2 Patient disposition

The following will be presented based on the Safety Set (SAF) in overall and the subpopulations defined in section 2.13.2.1 (whenever applicable):

- First 12 weeks of the first half of the treatment period (from Visit 201 to Visit 204, denoted as TRT1A): the number and percentage of participants who entered, completed,

and discontinued treatment prior to the Week 12 visit (including the reason for discontinuation)

- Week 12 to Week 24 of the first half of the treatment period (from Visit 204 to Visit 207, denoted as TRT1B-a): The number and percentage of participants who entered, completed, and discontinued from Week 12 up to Week 24 in the first half of the treatment period (including the reason for discontinuation)
- Week 24 to Week 52 of the first half of the treatment period (from Visit 207 to Visit 214 or 301, whichever comes first, denoted as TRT1B-b): The number and percentage of participants who entered, completed, and discontinued from Week 24 onwards in the first half of the treatment period (including the reason for discontinuation)

Duration of each study periods mentioned above will be summarized in overall and the subpopulations defined in Section 2.13.2.1 (whenever applicable). Duration in weeks will be calculated as (the date of the study period end date - the date of the study period start date + 1) / 7.

In addition, the following will be summarized:

- Number and proportion of participants in each subpopulation defined in Section 572.13.2.1.
- Number and proportion of each type of administration (listed in **Table 2-13**) at each visit, from Visit 204 (Week 12) to Visit 207 (Week 24) in the self-administration subpopulation only.
- Number and proportion of participants who receive at least 50% injections with PFS by participants herself/himself or a caregiver after Visit 207 (Week 24). This summary will be provided in the self-administration subpopulation only.

2.13.2.3.3 Study treatment / compliance

The analysis of treatment received will be performed based on the SAF for relevant study periods in overall and the subpopulations defined in Section 572.13.2.1. Categorical data will be summarized as frequencies and percentages. For continuous data, mean, standard deviation, median, 25th and 75th percentiles, minimum, and maximum will be presented.

The number of participants and the duration of exposure to each treatment will be as indicated in **Table 2-14**. Duration of exposure is defined as the date of the last treatment minus the date of first treatment in the extension study plus 4 weeks (28 days), specified as below.

- Duration of exposure of ligelizumab 72/120 mg q4w liquid in vial is defined as: the date of last injection of ligelizumab 72/120 mg q4w liquid in vial minus the date of the first injection of ligelizumab 72/120 mg q4w liquid in vial plus 28 days.
- Duration of exposure of ligelizumab 120 mg q4w (PFS, administered by site-staff/self/caregiver **in clinic**) between Week 12 and Week 24 is defined as: the date of last injection of ligelizumab 120 mg q4w PFS before Week 24 visit date minus the date of the first injection of ligelizumab 120 mg q4w PFS plus 28 days.

- Duration of exposure of ligelizumab 120 mg q4w (PFS, administered by site-staff/self/caregiver **in clinic or outside of clinic**) from Week 24 onwards up to data cut is defined as: the date of last injection of ligelizumab 120 mg q4w PFS by the cut-off date of this interim minus the date of the first injection of ligelizumab 120 mg q4w PFS since Week 24 visit date plus 28 days.
- Duration of exposure of ligelizumab (any ligelizumab treatment) up to data cut is defined as: the date of last injection of ligelizumab 72/120 mg q4w PFS by the cut-off date of this interim minus the date of the first injection of ligelizumab 72/120 mg q4w liquid in vial plus 28 days.

Visit on the cut-off date is included in the next study period. For example, Week 12 visit is included in the study period of Week 12 – Week 24. Missing visit on the cut-off date will be handled in different scenarios. The study period with missing visit on the cut-off date will be adjusted according to the missing reasons as specified below.

- Missing visit at Week 12:

Reason of missing visit at Week 12	Adjusted study period of “Up to Week 12”
Early discontinued during Week 0-12	From Week 0 to the day of discontinuation
Missed Week 12 visit and completed the next visit	From Week 0 to the day before PFS injection
Have not reached Week 12 visit yet	From Week 0 to the cut-off date of this interim

- Missing visit at Week 24:

Reason of missing visit at Week 24	Adjusted study period of “Week 12 – Week 24”
Early discontinued during Week 12-24	From Week 12 to the day of discontinuation
Missed Week 24 visit and completed the next visit	From Week 12 to the day before next injection
Have not reached Week 24 visit yet	From Week 12 to the cut-off date of this interim

In addition, the number of doses per patient that are correctly administered per protocol, and number of missed doses will be presented. A partial dose will be considered as if 100% of the dose of the assigned treatment has been administered.

Table 2-14 Treatment exposures evaluated in relevant study periods

Treatment	Study period
ligelizumab 72/120 mg q4w (LIVI)	Up to Week 12
ligelizumab 120 mg q4w (PFS, administered by site-staff/self/caregiver in clinic)	Week 12 – Week 24
ligelizumab 120 mg q4w (PFS, administered by site-staff/self/caregiver in clinic or outside of clinic)	Week 24 onwards (up to data cut off)
ligelizumab (any ligelizumab treatment)	entire study (up to data cut off)

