3.3 First half of the treatment period

- Week 0 (Visit 201) to Week 52
- Subjects receive their first dose of ligelizumab at Visit 201 (Week 0) and last dose of ligelizumab of this first half of the treatment period at Visit 213 (Week 48).
- Subjects must remain on the same H1-AH background medication they were taking in the preceding studies.
- Subjects should use the same H1-AH rescue medication that was agreed with the investigator at Visit 1 of this study.
- Oral corticosteroid rescue medication is permitted only at and after Visit 204 (Week 12) (after all assessments are completed), with the limitations as per protocol (see [Section 6.2.3](#)).
- Subjects entering the first half of the treatment period from the preceding studies will be assigned to treatment as follows:
 - Core studies CQGE031C2302 and CQGE031C2303:
 - For the first 12 weeks, the blinded treatment assignment will be determined according to the treatment group assignment during the core studies following these rules:
 - Subjects treated with ligelizumab 72 mg liquid in vial s.c. q4w in the core studies will be treated with ligelizumab 72 mg liquid in vial s.c. q4w in a double-blind manner such that their prior treatment regimen will not be unblinded.
 - All other subjects from the core studies will be treated with ligelizumab 120 mg liquid in vial s.c. q4w in a double-blind manner such that their prior treatment regimen will not be unblinded.

- Studies CQGE031C1301 and CQGE031C2202:
 - All subjects from these studies will be treated with ligelizumab 120 mg liquid in vial s.c. q4w in an open-label manner for the first 12 weeks.
- If the subject in the screening period or first observation period presents with moderate to severe disease, defined as $UAS7 \geq 16$, the subject will enter the treatment period at Visit 201 (Week 0), and start the treatment assigned as above.
- At Visit 204 (Week 12), all subjects will be switched to ligelizumab 120 mg s.c. pre-filled syringe (PFS) q4w in an open-label manner.
- At Visit 204 (Week 12) subjects will be offered an opportunity to administer ligelizumab outside the clinic. For details regarding self-administration outside of the clinic and monitoring post ligelizumab administration, see [Section 6.7.2](#).
- All subjects, whether in the clinic-administered or outside the clinic self-administered group will continue to complete the eDiary twice daily as per protocol.

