2.13.2.1 Interim analysis set(s)

The Safety analysis set (SAF), as defined in Section 2.2, including all subjects who received at least one dose of study treatment will be used for all the analyses of this interim analysis.

Three types of administration defined in Table 2-13 are of interest in this interim analysis. The following subpopulations according to those types of administration will be considered in the safety and efficacy analyses for this interim analysis:

- **Outside-of-clinic self-administration:** participants who have at least one outside-of-clinic injection with PFS administered by either the participant herself/himself or a caregiver.
- **Self-administration:** participants who have at least one injection with PFS administered by the participant herself/himself or a caregiver either in clinic or outside of clinic.
- **In-clinic staff-administration:** participants who have all injections with PFS administered in clinic and by the site staff.

Definition of the above three subpopulations only depends on data in the first half of the treatment period. For example, participants who have all injections done in-clinic and by site staff in the first half of the treatment period, and start self-administration in the second half of the treatment period would belong to the in-clinic staff-administration subpopulation for the purpose of this interim analysis.

Table 2-13 Definition of type of administration

Type of administration	Definition
Outside-of-clinic self-administration	Outside-of-clinic injections with PFS administered by either the participant herself/himself or a caregiver
Self-administration	Injections with PFS administered by the participant herself/himself or a caregiver either in clinic or outside of clinic

In-clinic staff-administration	Injections with PFS administered in clinic and by the site staff
--------------------------------	--

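### In the unplanned interim, the overall ligelizumab exposure row ends at the last PFS injection, so treated subjects who had only liquid in vial get no exposure value

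*SAP*

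**What the plan says.** SAP 2.13.2.3.3 opens with a general rule for duration of exposure: "the date of the last treatment minus the date of first treatment in the extension study plus 4 weeks (28 days), specified as below". Four bullets follow, matching the rows of Table 2-14. The last covers any ligelizumab treatment up to the data cut. It ends exposure at "the date of last injection of ligelizumab 72/120 mg q4w PFS by the cut-off date of this interim", then continues "minus the date of the first injection of ligelizumab 72/120 mg q4w liquid in vial plus 28 days". It has no branch for a subject without a PFS injection.

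SAP 2.13.2.1 takes the Safety Set for this interim, "including all subjects who received at least one dose of study treatment will be used for all the analyses of this interim analysis". The missing-visit rules in 2.13.2.3.3 expect some of these subjects to be short of PFS. They list subjects who discontinued between Weeks 0 and 12, and subjects described as "Have not reached Week 12 visit yet".

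Protocol 3.3 places the change of presentation at Week 12, when "all subjects will be switched to ligelizumab 120 mg s.c. pre-filled syringe (PFS) q4w in an open-label manner". Protocol 6.6.1 makes the first three treatment visits liquid in vial. Protocol 6.1 and Table 6-1 list the PFS in one strength, 120 mg.

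**The concern.** The bullet uses a PFS date for a row meant to cover all ligelizumab, and it names a 72 mg PFS that the study does not supply. A subject with only liquid-in-vial doses has a start date but no end date.

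These are the shortest exposures in the Safety Set. If they drop out of the row, its N no longer matches the set it is said to describe, and the distribution loses its lower end. The section asks for mean, standard deviation, median, quartiles, minimum and maximum, and the missing subjects can affect all of these except the maximum. This interim was written to support a licence submission (SAP 2.13.2). SAP 2.8.1.3 says that the PFS self-administration safety analyses were done at the interim and will not be repeated, so the overall exposure table in that report would not be superseded by a rerun of the interim.

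**Working it through.** The SAP states no exposure figure, so there is none to reproduce. The check applies the bullet and the general rule to the planned schedule.

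**Inputs**
- Days counted from first dose. Liquid in vial on days 0, 28 and 56; PFS from day 84, every 28 days (Protocol 3.3, 6.1.3, 6.6.1).
- Bullet: last PFS injection on or before the cut − first vial injection + 28.
- General rule: last injection of either presentation − first injection + 28.

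**Step 1. Values under each rule**

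| Doses received | Last injection (day) | General rule | Bullet |
|---|---|---|---|
| 1 (vial) | 0 | 0 − 0 + 28 = 28 | none |
| 2 (vial) | 28 | 28 − 0 + 28 = 56 | none |
| 3 (vial) | 56 | 56 − 0 + 28 = 84 | none |
| 4 (first PFS) | 84 | 84 − 0 + 28 = 112 | 112 |

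From the fourth dose on, the two rules agree. On schedule, the smallest value the bullet can return is 112 days; the smallest the general rule can return is 28.

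**Step 2. Effect on the overall row**

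Let s be the share of the Safety Set with vial doses only, M_V their mean exposure and M_P the mean of those with at least one PFS dose.
- N in the row = (1 − s) × N of the Safety Set.
- Mean reported by the bullet = M_P. Mean under the general rule = (1 − s) × M_P + s × M_V.
- Difference = s × (M_P − M_V).

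On schedule M_P is at least 112 and M_V at most 84, so the difference is at least 28 × s days and always upward. Total person-time moves the other way, because the omitted subjects contribute nothing to the sum.

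The documents do not give s. For illustration only, take the planning drop-out before Week 12: 10% in SAP Table 3-1 and 15% in the text before Table 3-2. Suppose all of these subjects stop before the first PFS dose. Then 50 to 75 of every 500 subjects have no value, and the mean is too high by at least 28 × 0.10 = 2.8 to 28 × 0.15 = 4.2 days. Subjects not yet at Week 12 at the cut would add to s. The upper end cannot be stated without M_P and M_V.

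**Step 3. The added 28 days at the cut-off**

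If the last injection is k days before the cut, the last credited day falls 27 − k days after it, for k = 0 to 26. For k of 27 or more there is no overrun. The maximum is 27 calendar days. A subject injected on the cut date is credited 112 days against 85 up to the cut at Week 12, and 364 against 337 at Week 48.

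**The case against.** The strongest reply is that nobody would read the bullet literally. The general rule in the same section gives every treated subject a value, the bullet is labelled as any ligelizumab treatment, and a 72 mg PFS does not exist, so the author must have meant the last injection of either presentation. Vial-only subjects also keep a value in the separate liquid-in-vial row. All of this is fair, and it makes the intent easy to guess. But the general rule says that the bullets specify it, so a programmer working from the bullet would produce the defective row. The two statements have to be made to agree.

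Three stronger readings are tempting, and the documents do not support them.

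- A reader might infer that the 28 days added beyond the cut are an error. Last dose plus 28 days is the exposure convention in Protocol 12.3 and SAP 2.4.1, and the bullet's reference to the cut-off limits which injections count. What remains is that two rows of Table 2-14 are labelled as running up to the cut, which calls for a footnote.
- A reader might infer that adverse-event rates are distorted. SAP 2.8.1.2 computes the exposure-adjusted rate from time to first event or last follow-up, and 2.13.2.5.2 does not tie it to this duration. Crude incidence uses subject counts.
- A reader might put a percentage on the overstatement of mean exposure. That needs group means and a share of vial-only subjects that the documents do not contain.

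The scope is also narrow. Both self-administration subpopulations require at least one PFS injection. The final analysis follows SAP 2.4.1, which uses last minus first treatment plus 28 days. The study has since been terminated, so no remaining planned analysis depends on the bullet.

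**Conclusion.** The bullet is wrong as written, and the point is minor. It contradicts the general rule it is meant to specify, and it gives no value to Safety Set subjects who had only liquid in vial. Followed literally, the overall row has too small an N, a smallest possible on-schedule value of 112 days instead of 28, and a mean and quartiles biased upward. The direction of the mean bias needs only the planned schedule and at least one vial-only subject. Its size depends on a share that is not stated.

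The conclusion is confined to the overall row of the unplanned interim. It assumes that the table was programmed from the bullet, which the documents do not show.

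**What to change.** 1. Redefine the row as the date of the last injection of any ligelizumab (liquid in vial 72 mg or 120 mg, or PFS 120 mg) on or before the cut-off, minus the date of the first injection, plus 28 days.
2. Delete the 72 mg from the PFS wording.
3. Find out which rule the interim program used. If it followed the bullet, re-run the overall row or footnote it with the number of vial-only subjects omitted. The check is whether the row's N equals the Safety Set.
4. Footnote the two Table 2-14 rows that are labelled up to the data cut: the 28-day convention can credit up to 27 calendar days beyond the cut for subjects injected shortly before it. Truncating at the cut is an option, not a correction; if chosen, apply it to both rows.

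The cost is one sentence, one footnote and, at most, a re-run of one exposure table. If the bullet was followed, the corrected row will show a larger N and a lower mean.

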2.13.2.4 Efficacy analyses at interim analysis: variables and type of analysis

No inferential statistical methods are planned for this interim analysis. Descriptive statistics will be used to summarize the following efficacy endpoints in the subpopulations defined in Section 2.13.2.1 at baseline, Week 4, 8, 12, 16, 20, 24, 28, 32, 36, 42, 44, 48, and 52:

- Change from extension study baseline and 95% confidence intervals in UAS7/ISS7/HSS7 score, based on the observed data.
- Number and proportion of participants who achieve UAS7=0/UAS7≤6/HSS7=0/ISS7=0 response, based on the observed data.

Separate tables will be provide for LIVI (baseline, Week 4, 8, 12) and PFS (Week 12 onwards).

2.13.2.5 Safety analyses at interim analysis: variables and type of analysis

To assess the safety and tolerability of ligelizumab, adverse events (AEs) will be summarized in the safety set.

2.13.2.5.1 General information

Only treatment emergent adverse events (TEAEs) will be considered. All TEAEs reported will coded using MedDRA terminology and summarized by primary System Organ Class (SOC) and Preferred Term (PT) in the overall population and the subpopulations defined in Section 2.13.2.1.

Non-treatment emergent AEs by study period (including observation period 1) will only be listed and not further summarized.

TEAEs will be summarized by actual received treatment, in relevant treatment periods (see Table 2-15) for each subpopulation defined in Section 2.13.2.1.

TEAEs are defined as:

- Events starting after the first dose of study treatment (ligelizumab) in the extension study and within 16 weeks of last dose of study treatment
- Events present prior to the first dose of study treatment (ligelizumab) in the extension study but:
 - increase in severity based on preferred term (e.g. worsening of headache),
 - same PT but increased severity (e.g. from mild to moderate),
 - same PT but increase in seriousness (from non-serious AE to SAE; if already a SAE from medically significant to life-threatening/fatal)

Within a specific treatment period, a subject with multiple AEs within a primary system organ class will be counted only once for the primary SOC, with the greatest severity at the system organ class level displayed.

The following Treatment emergent AEs of special interest (TEAESIs) defined in the compound-level electronic Case Retrieval Strategy (eCRS) will be presented up to SMQ level 5. The search criteria in the latest eCRS and the corresponding MedDRA version at the database lock will be used for reporting:

- Hypersensitivity reactions (including anaphylaxis)
- Injection site reactions
- Serum sickness

For AESIs with adjudication, separate listing(s) will be provided based on the adjudicated results.

2.13.2.5.2 Crude and Exposure-Adjusted Incidence Rate

[figure not shown]
The crude incidence rate and EAIR are defined in Section 2.8.1.2, with formula $EAIR = n / \sum t_i$, where n is the number of subjects having the i^{th} type event in the corresponding study period (defined in Table 2-14), and t_i is a subject's exposure time until having an i^{th} type event. For TEAE possibly related to study treatment, n is the number of subjects having the i^{th} type event possibly related to study treatment in the corresponding study period (defined in Table 2-14), and t_i is a subject's exposure time until having an i^{th} type event possibly related to study treatment. As described in Table 2-15, the exposure-adjusted incidence rate (EAIR) will be provided for the safety analysis in certain study periods in addition to the crude rate.

[figure not shown]
In this interim analysis, whenever applicable, exposure adjusted incidence rates will be provided for the type as below:

1. TEAE: Primary SOC level and preferred term level
2. Treatment emergent AE of special interest: up to SMQ level 5

2.13.2.5.3 AE summaries

Table 2-15 in Section 2.13.2.8 lists the summaries tables and listings that will be provided for TEAE, treatment emergent SAE, treatment emergent AESI in the study periods defined in Table 2-14.

[figure not shown]

2.13.2.8 Overview of unplanned interim analysis

Table 2-15 Overview of unplanned interim analysis

Population/ Analysis /Study Period	Endpoints

Analysis: Efficacy
 
Population:
 
SAF
 
Outside-of-clinic self-administration subpopulation
 
Self-administration subpopulation
 
In-clinic staff-administration subpopulation
 
Study period:
 
TRT1
	
 • Proportion of subjects with well-controlled urticaria (UAS7 ≤ 6) by visit • The proportion of subjects with completely controlled disease (UAS7 = 0) by visit • The proportion of subjects with ISS7 = 0 by visit • The proportion of subjects with HSS7 = 0 by visit • Absolute change from extension study baseline in the UAS7 and its components (ISS7 and HSS7) by visit 
█ [REDACTED]

Analysis: Safety
 
Population:
 
SAF
 
Outside-of-clinic self-administration subpopulation
 
Self-administration subpopulation
 
In-clinic staff-administration subpopulation
 
Study period:
 
Week 0—12 in TRT1
 
Week 12—24 in TRT1
 
Week 24 onwards up to interim data cut off
 
Entire study up to interim data cut off
	
The crude incidence and exposure adjusted incidence will be provided for:
 
 • TEAE • Study treatment related TEAE • TESAE • TEAESI • TEAEs leading to discontinuation 
Other:
 
 • Listing of TEAEs leading to drug interruption • Crude incidence of TEAE by severity • Listing of adjudicated AE

